Despite increased awareness of T2DM and its risk factors, the incidence of this disorder is growing, especially in younger adults. Short sleep duration has been identified as an independent risk factor for IR and T2DM; however, few lay persons are aware of this finding. Innovative and easily implemented primary prevention efforts are needed to prevent progression of disease in those with IR, a precursor to T2DM, and addressing sleep deprivation may be one effective method. We know that development of T2DM is complex and can involve multiple factors. Our participants will have the T2DM risk factors of IR, obesity and short sleep duration, but we are focusing our attention on extending sleep duration while not intervening with nutrition, physical activity and body weight in order to better evaluate the efficacy of our sleep intervention. If our results show this tailored sleep intervention (SLEEP-Extend) is feasible and does extend sleep duration as well as provide preliminary evidence of improved IR levels in sleep-deprived young adults at risk for T2DM, then we will have a foundation for a larger study to test the efficacy of SLEEP-Extend. Additionally, this initial SLEEP-Extend intervention will be a relatively low-cost approach to reduce this one risk factor (short sleep) of T2DM. The study will provide evidence of impact in intervening with sleep duration to improve metabolic function. Only one study has explored sleep extension as an intervention for short sleep duration and studied the effects on

glucose metabolism, and no sleep extension studies were found in a population at risk for T2DM. Based on the lack of evidence, little is known about how extending sleep will impact IR.

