## **Objectives**

**Aims:** The aims for this pilot study of young adults ages 18-25 years old with IR (based on established cut points), short sleep (< 7 hours/night) and obesity (BMI  $\geq$  30) are to: 1) evaluate the feasibility and acceptability of a tailored intervention to extend sleep duration (SLEEP-Extend), 2) determine changes in sleep duration after SLEEP-Extend intervention, 3) evaluate IR levels before and after SLEEP-Extend, and 4) explore the potential mediators of diet and physical activity between sleep duration and IR. Our hypotheses are: H1: Individuals undergoing SLEEP-Extend will have longer sleep duration and increased knowledge of sleep hygiene post-intervention compared to controls and, H2: A greater proportion of the SLEEP-Extend group will have a decrease in IR compared to the control group.

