### **Outcome Measures:**

**BMI and baseline blood samples will be obtained at the screening visit.** All other measures will be assessed at the baseline visit and at the end of the 4-week intervention period except for the following: 1) Actigraphy watch will be worn continuously, and daily sleep diary completed for the entire study period, 2) The sleep hygiene pre/post-test and safety pre/post-test (control group only) will be given prior to intervention, immediately post intervention and at end of 4-week intervention period (3 time points), 3) Participant characteristics questionnaire only at baseline, and 4) Both groups will receive the exit survey at end of 4 week intervention period. **Insulin Resistance:** A) Glucose and insulin levels will be measured from fasting serum samples. B) Insulin Resistance will be calculated from the measured glucose and insulin levels using standard formulas. Briefly, serum samples will be collected via venipuncture and analyzed at Cardiovascular Specialty Laboratories, Inc (Atlanta, GA) using standard laboratory approaches with calibrated equipment (See letters of cooperation, from [name] and [name]). These two values will be used to calculate the homeostatic model assessment of insulin resistance (HOMA-IR; blood glucose level X insulin level, divided by 22.5). Elevated values indicate IR. A cutoff score of HOMA-IR < 2.1 as normal and HOMA-IR  $\geq$  2.1 as elevated (evidence of IR) will be used as determined in non-diabetics (Esteghamati et al., 2010). **Sleep Duration:** Using wrist actigraphy (Motionlogger, AMI, Ardsley, NY) along with a sleep diary (required to help validate and score actigraphy data; Martin & Hakim, 2011), we will objectively monitor each participant's 24-hour sleep-wake cycle to obtain average sleep duration (total sleep time) for one week (baseline) prior to random assignment to group and will continue monitoring during the 4 week intervention period. All participants wear the device (looks like a watch) on the wrist continuously for a total of 5 weeks (1 week for baseline sleep and 4 weeks of intervention period), except while bathing or swimming. Leproult and colleagues (2015) had success with adults wearing a wrist actigraph continuously for a total of 8 weeks. This device contains a light sensor that stores activity counts in 1-minute epochs and will detect the onset and offset of sleep using concurrent data from sleep diaries (Buysse et al., 2008; Morgenthaler et al., 2007). The Motionlogger was successfully validated against polysomnography on dimensions of sleep patterns: sleep onset latency, wake time after sleep onset, total sleep time (sleep duration), and sleep efficiency percentage (Cole et al., 1992). Data for each sleep component will be averaged over the 7 days for each week of the protocol (e.g. average sleep efficiency percentage, average total sleep duration) for analysis. Actigraphy has been compared to polysomnography to detect sleep and wakefulness and found to have a sensitivity of .965 and accuracy of .863 (Marino et al., 2013). The sleep diary is necessary to record data to help interpret actigraphy data (time in bed, time awake, and anything that occurs during the night such as waking up in the middle of the night). Participants in the SLEEP-Extend group will also use a daily sleep diary to record any sleep hygiene practices they use. Participants in the control group will use the same daily sleep diary as the SLEEP-Extend group with the difference of recording any safety practices used rather than recording sleep hygiene practices used. **Sleep Hygiene Knowledge:** To assess

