
the fidelity of the intervention, we are including a sleep hygiene test that will be given at 3 time points: as a pre-test, and as a post-test immediately after the education and at the end of the 4-week intervention period. The researcher-developed sleep hygiene questionnaire is based on the sleep hygiene recommendations from the NSF and the American Academy of Sleep Medicine (AASM). Participants will identify true or false if an item is recommended to facilitate sleep. Non-sleep hygiene items will be included. In addition, the control group will receive an investigator-developed instrument with the list of safety practices based on safety information they receive. Both instruments will be reviewed for content validity by a content expert and researcher with measurement expertise. **Physical activity and Dietary characteristics:** Physical activity will be measured by activity levels from the actigraphy monitor as well as self-report using the Baecke questionnaire (Baecke, Burema & Frijters, 1982). Dietary habits will be measured by self-report using the 26-item Dietary Screener (National Cancer Institute, 2015). Both the Baecke questionnaire and Dietary Screener have evidence of validity (Philippaerts, Westerterp, & Lefevre 1999; Thompson et al, 2005). Diet and physical activity are also reported to impact IR, and a recent study found that in adolescent girls, poorer diet and lower physical activity were associated with higher levels of IR (Jiménez-Pavón et al, 2013). Measuring this at baseline and after the 4-week intervention period will allow us to assess if dietary and/or physical activity were mediators between sleep duration and IR. **Adherence to the intervention:** The percent of days extending time in bed will be computed from the total number of days TIB was actually extended by one hour over the total intervention days (4 weeks = 28 days). **Exit Interview:** Participants in both groups will be interviewed after the 4-week intervention period. This investigator-developed interview will assess their satisfaction with the intervention, any difficulties implementing the intervention strategies and what they felt was most effective and if they would recommend others to participate in the intervention. The interview questions will be reviewed by a content expert and researcher with measurement expertise. **Participant Characteristics:** Will be assessed at baseline via an investigator-developed questionnaire which will include T2DM risk factors based on the ADA risk assessment tool [male gender, family history of diabetes, high blood pressure, and physical inactivity (ADA, Are you at risk?)]. Additional data will include age, marital status, and factors that may affect sleep and/or glucose/insulin levels such as work hours, health problems, and medications. Calculation of BMI from height (stadiometer) and weight (calibrated scale) using a standard formula will be obtained. These data will describe the sample, and a total T2DM risk factor score will be calculated by summing the number of risk factors. Other data will be evaluated as potential covariates. BMI will be assessed at screening and at the end of the 4 week intervention period in both groups.

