4. Visit #1 (screening visit) will include obtaining blood samples to calculate insulin resistance, 2 consecutive nights of pulse oximetry and one week of baseline sleep duration using Actigraphy monitoring. The researcher will meet the subject in a private room located on the university campus and will conduct explanation of consent.
- a. The researcher or GRA will obtain written informed consent and a copy provided to the subject.
  - b. The researcher will confirm the subject has not had anything to eat or drink in the past 10 hours
  - c. A registered nurse (either the researcher or GRA) will obtain the following
    - i. Blood sample will be obtained using standard protocol with universal precautions to obtain fasting serum blood glucose and plasma insulin levels. These levels will be used to calculate insulin resistance. A registered nurse will pierce the subject's skin (usually in a vein located on the inside middle part of the arm) with a very small needle and take the blood into a small tube. This method of taking blood is called a venipuncture. The total amount of blood drawn is about 5 ml or 1 teaspoon. During the blood draw, the subject will feel a pinch that lasts several seconds when the blood sample is taken. The subject may have pain, dizziness, bleeding, or bruising at the site of the blood draw. There is a slight risk of infection and scarring at the site of the blood draw. However, the registered nurse will use proper technique while taking the blood sample in order to reduce unwanted effects.
    - ii. After obtaining the blood sample, the subject will be offered a light snack (granola bar, crackers or cookies) to eat and water or juice to drink.

- iii. Subject blood samples will be labeled using a unique identification number and will be stored in a secure laboratory at Emory University until they can be analyzed by Cardiovascular Specialty Laboratories, Inc. in Atlanta, GA. The blood samples will be destroyed by Cardiovascular Specialty Laboratories, Inc. once analysis of blood levels is completed. IBC protocol submitted and approval is pending.
- d. The researcher or GRA will obtain and instruct in the following:
  - i. Subject height (using a stadiometer) without shoes
  - ii. Subject weight (using a calibrated scale) in light clothing and no shoes
  - iii. Subject body fat analysis (using a hand-held, non-invasive calibrated scale) (Omron Body Logic Pro, Omron Healthcare, Inc., Vernon Hills, IL

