- e. After one week of baseline actigraphy and pulse oximetry monitoring, the subject will return the actigraph and pulse oximeter and data will be downloaded and analyzed for sleep duration and oxygen saturation respectively. The researcher or GRA will access sleep diary information from the SleepBot app by taking a screen-shot of the data and printing it. Sleep diary info on the screen-shot will be deleted and only a paper version of the sleep diary will be retained. If the subject used a paper sleep diary, then it will be returned to the researcher for analysis.
- f. If the subject's average sleep duration is not below 7 hours per night or their insulin resistance level does not meet the inclusion criteria (HOMA-IR is a measure of insulin

resistance and needs to be  $\geq 2.1$  in order to meet inclusion criteria), or if their oxygen desaturation index is  $\geq 5$ /hour they will be thanked for their interest and told they are not eligible for the study. Additionally, if the subject's oxygen desaturation index is  $\geq 5$ /hour, they will be instructed to follow up with a health provider for assessment of possible OSA.

- g. If the subject's average sleep duration is less than 7 hours per night and their HOMA-IR meets inclusion criteria ( $\geq 2.1$ ) and their oxygen desaturation index is  $< 5$ /hour, then the subject will be scheduled for their study enrollment visit (Visit #2) to collect questionnaires/surveys. Subjects will be given \$10 after the screening visit.
5. Visit #2 (Study Enrollment Visit): This visit is done as soon as possible following screening. The researcher or GRA will meet the subject in a private room located on the university campus. The study enrollment visit for all subjects includes randomization to the treatment or control group and completion of:
  - a. Researcher-developed demographic/subject characteristics questionnaire
  - b. Baecke physical activity questionnaire
  - c. Dietary Screener questionnaire
  - d. Meal Timing questionnaire
  - e. Perceived Stress Scale
  - f. Sleep Hygiene Index questionnaire
  - g. Control group only: an investigator-developed safety practices questionnaire
  - h. Each subject will be asked to wear the actigraphy watch continuously for 4 additional weeks and complete daily sleep diary for 4 additional weeks (as previously discussed).
  - i. The intervention will be administered as follows

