### **Analysis Plan**

Data analysis will include descriptive statistics to characterize the sample and inferential statistics to compare study variables. Sleep characteristics will be expressed as percent change from beginning to end and analyzed with repeat measures ANOVA. Blood levels will also be expressed as percent change from baseline to last draw. Correlational analysis will be used with sleep variables and IR. Regression analysis including components of sleep, BMI, dietary and physical activity will be conducted to examine the association of sleep factors and IR. Responses to the exit interview questions will be content coded and interrater reliability assessed.

- 3. Data and Safety Monitoring and Reporting: If there is an adverse or reportable event, the IRB will be notified promptly via the eIRB reportable event form. Also, the event will be documented in a tracking log. The sponsor does not require reporting above and beyond Emory IRB reporting requirements. This study does not include more than minimal risk; however, the PI will periodically review documentation to ensure accuracy and completeness.

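### The actigraphy week that must average under 7 hours is also the only baseline, so sleep rises in both arms by regression to the mean; the Analysis Plan should name the baseline-adjusted between-arm difference

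*Combined protocol and SAP*

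**What the plan says.** **Entry gate and baseline.** In Informed Consent Process and Visit Details, item 4, Visit #1 includes "one week of baseline sleep duration using Actigraphy monitoring". Items 4.f and 4.g use that week to decide eligibility: candidates proceed only if their "average sleep duration is less than 7 hours per night". Those enrolled are randomised at Visit #2 and asked to "wear the actigraphy watch continuously for 4 additional weeks". No second baseline is taken. Outcome Measures defines the baseline as "average sleep duration (total sleep time) for one week (baseline) prior to random assignment to group".

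**Aim and hypothesis.** Aim 2 in Objectives is to "determine changes in sleep duration after SLEEP-Extend intervention", with no comparator. H1, stated directly after the aims, is between-arm: sleep after the intervention is expected to be longer than in controls.

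**Analysis.** The Analysis Plan says: "Sleep characteristics will be expressed as percent change from beginning to end and analyzed with repeat measures ANOVA". It names no group term, group-by-time contrast or baseline adjustment.

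**A conflicting flow.** The inclusion criteria under Study Methods require only self-reported short sleep. PROCEDURES issues the watch at Visit #2, after eligibility has been settled. In that flow the actigraphy week does not select anyone.

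**The concern.** A seven-night mean is a noisy measure of habitual sleep. If candidates are kept only when that mean falls below a limit, some are kept because the week was short by chance. Their later weeks then average longer with no change in behaviour. When the same week is the reference for change, this shift appears as a gain.

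An analyst following the Analysis Plan literally could report the percent change within the SLEEP-Extend arm, or the ANOVA time effect, as the answer to Aim 2. Either would include the shift. The pilot is meant to inform a decision on a larger study, so an inflated sleep gain could carry into that decision.

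**Working it through.** **Inputs.** From the documents: the limit of 7 h (420 min), seven-night averaging, 10 participants per arm, four intervention weeks, and randomisation after the qualifying week. The documents give no SD, no candidate mean and no effect size, so there is no stated figure to reproduce. Assumed: between-person SD 45 min; night-to-night SD 60, 75 or 90 min; candidates' true mean 6.0, 6.5 or 7.0 h (360, 390 or 420 min); independent nights; no true change.

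**Formula.** Let X be the baseline-week mean, with mean μ and SD s = √(45² + σ²/7), where σ is the night SD. The reliability of X is ρ = 45²/s². With a = (420 − μ)/s and λ = φ(a)/Φ(a):

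- mean baseline among those admitted = μ − sλ
- expected rise with no behaviour change = (1 − ρ)sλ

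**Worked case (μ = 390, σ = 75).**

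- s = √(2025 + 803.6) = 53.2
- ρ = 2025/2828.6 = 0.716
- a = 30/53.2 = 0.564
- λ = 0.3403/0.7136 = 0.477
- admitted baseline mean = 390 − 25.4 = 364.6 min
- rise = 0.284 × 25.4 = 7.2 min, or 7.2/364.6 = 2.0%

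**Expected rise in minutes:**

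| Candidate mean | Night SD 60 | Night SD 75 | Night SD 90 |
|---|---|---|---|
| 6.0 h | 2.3 | 3.7 | 5.4 |
| 6.5 h | 4.7 | 7.2 | 10.1 |
| 7.0 h | 8.1 | 12.1 | 16.4 |

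As a share of the admitted baseline mean, the range is 2.3/348.8 = 0.7% to 16.4/375.0 = 4.4%. A wider grid (ρ from 0.50 to 0.90, mean 6.0-7.5 h) gives 1.5 to 34 min. Every setting stays below the 60-min target.

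**Effect on a within-arm test.** Trials were simulated under the SDs above with no true change, and the upper-tail rejection rate of a paired t-test was counted (nominal 2.5%). For one arm of 10 and a candidate mean of 6.5-7.0 h, it was 6-17% using week 4 and 8-26% using the mean of 28 nights. At a candidate mean of 6.0 h, a rerun of 6,000 trials per setting gave about 4-6%.

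**Effect on the between-arm test.** Both arms pass through the same gate before randomisation, so the expected rise is equal and cancels. In simulations with no effect, the between-arm difference in mean change averaged −0.2 to +0.2 min, and the two-sided test rejected 4.5-5.3% of the time against a nominal 5%.

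**Adherence.** Outcome Measures counts the "total number of days TIB was actually extended by one hour over the total intervention days". It does not name the reference week or restrict the calculation to one arm. If the baseline week is the reference, and sleep efficiency is assumed to be 0.87, the share of nights at least one hour above it in someone who changed nothing is 20.7-29.4% with an unselected week and 22.8-35.3% with the gated week (candidate mean 6.5-7.0 h). Most of that share is ordinary night-to-night variation; the gate adds about 2-6 points.

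**The case against.** The strongest reply is that this is a randomised trial with an attention control, and the only hypothesis on sleep duration, H1, compares with that control. If both arms drift up equally, H1 is not supported, however the aim is phrased. This stands: the randomised comparison is not biased.

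The size is also uncertain. Candidates are already pre-screened by telephone on self-reported short sleep, so a true mean near 6.0 h is plausible and the rise may be only 2-5 min. Seven-night averaging limits it further. This stands too.

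Four stronger readings are tempting, and the documents do not support them:

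- *Aim 2 can be met by the selection rule alone.* That requires reading Aim 2 without the hypothesis stated beside it.
- *The case for a larger study rests on change from baseline.* The Introduction asks whether the intervention "does extend sleep duration as well as provide preliminary evidence of improved IR levels". It mentions neither baseline nor change, and in this design the control arm tests such a claim.
- *A pooled time effect will be taken as proof of extension.* Pooling both arms gives larger simulated error rates (about 9-33% at week 4, again for a mean of 6.5-7.0 h), but no section says the pooled effect will be read that way.
- *Adherence is counted in one arm against the gated week.* The text specifies neither.

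What the reply leaves open is the Analysis Plan. It does not connect the H1 contrast to the stated analysis, and percent change from the gated week remains the only sleep measure it specifies.

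**Conclusion.** The concern holds in a limited form. If the Visit Details flow is followed, sleep duration is expected to rise in both arms by about 2-16 min with no behaviour change, under the assumed SDs and a candidate mean of 6.0-7.0 h. That is 2.3/60 = 4% to 16.4/60 = 27% of the one-hour target. It cannot imitate full success, but it could make a modest within-arm gain look real. H1's comparison with controls is unaffected. The weakness is that Aim 2 has no comparator and the Analysis Plan names neither a between-arm contrast nor a baseline adjustment. Under the Study Methods and PROCEDURES flow the mechanism largely disappears. Severity is minor to moderate, as a weakness in the chosen analysis.

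**What to change.** 1. In the Analysis Plan, replace percent change for sleep duration with the SLEEP-Extend minus control difference in mean sleep duration over the four intervention weeks, adjusted for the baseline week (ANCOVA). Name this as the test for Aim 2 and H1.
2. State that within-arm change and the ANOVA time effect are descriptive and are not evidence of extension, because the baseline week was also the entry gate.
3. Reconcile Study Methods and PROCEDURES with Informed Consent Process and Visit Details on how short sleep is established and when the baseline week falls.
4. Optionally, report the share of nights with time in bed at least one hour above baseline in the control arm as well, as a reference for adherence.

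The cost is protocol wording and, if item 4 is adopted, one extra summary. Both arms already wear the watch and keep the diary, so no new data are needed. The downside is precision: with equal arms and equal variances, an unadjusted between-arm difference has a standard error √2 = 1.4 times that of a single-arm change. With 10 per arm, baseline adjustment recovers only a modest part of this at best.
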